## 3.3 Exploratory Objectives

- To characterize concordance rates between UC patient detected tumor, urine, and circulating free plasma FGFR3 mutations.
- To characterize associations between pre-treatment germline (as assessed by PBMC extracted DNA) FGFR SNPs and post-treatment 6-month complete response rate and 1-year relapse free survival rate in patients treated with dovitinib.
- To characterize associations between pre-treatment germline (as assessed by PBMC extracted DNA) VEGFR SNPs and post-treatment 6-month complete response rate and 1-year relapse free survival rate in patients treated with dovitinib.

- To characterize VEGFR over-expression status within tumor tissue
- To characterize pre- and post-treatment bladder tumor FGFR and VEGFR pathway phosphorylation changes as assessed by bladder tumor tissue immunohistochemistry.
- To characterize post-treatment bladder tissue dovitinib concentrations.
- To characterize associations between post-treatment hypertension, 6-month complete response rate and 1-year relapse free survival rate in patients treated with dovitinib.

### 3.3.1 Endpoint for Exploratory Objectives

- Presence of FGFR3 mutations (see Table 1-2) in tumor tissue and urine will be assessed by massively parallel sequencing of exons 7, 10, and 15 utilizing the Ion Torrent PGM instrument. Presence of FGFR3 mutations within patient free plasma will be assessed by PCR-amplification of the target regions and sequencing.
- Pre-treatment germline FGFR SNPs will be assessed by testing extracted DNA from patient PBMC's (collected prior to initiating dovitinib therapy) with validated commercial probes.
- Pre-treatment germline VEGFR SNPs will be assessed by testing extracted DNA from patient PBMC's (collected prior to initiating dovitinib therapy) with validated commercial probes.
- Presence of VEGFR over-expression within tumor tissue will be assessed and interpreted by standard immunohistochemistry analysis with appropriate controls.
- Pre- and post-treatment bladder tumor FGFR and VEGFR pathway phosphorylation changes will be assessed by bladder tumor tissue immunohistochemistry utilizing commercially available antibodies including, but not limited to, the following: FGFR3, pFGFR3, VEGFR2, pVEGFR2, FRS2, pFRS2, ERK, pERK.
- Post-treatment bladder tissue dovitinib concentrations will be assessed by TURBT fresh frozen tissue obtained at the 3-month cystoscopy
- Hypertension will be defined as a systolic blood pressure (SBP) of  $\geq 140$  mmHg or a diastolic blood pressure (DBP) of  $\geq 90$  mm Hg recorded at any time after dovitinib therapy is initiated.

Objectives and related endpoints are described in [Table 3-1](#) below.

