Biomarkers predictive of clinical efficacy and toxicity are emerging for VEGF directed therapies. In a recent randomized placebo-controlled phase III study (ECOG 2100) of paclitaxel plus bevacizumab (a recombinant humanized monoclonal antibody to VEGF) in the first-line treatment of metastatic breast cancer, patients who received bevacizumab demonstrated a significant prolongation of progression free survival (11.8 vs. 5.9 months, HR=0.60 p=0.001) (Miller et al., 2007). When the entire study population was analyzed (n=772), no significant differences in median overall survival were observed between patients who received bevacizumab and those who received placebo (26.7 months vs. 25.2 months, HR 0.88 p=0.15). In a planned biomarker analysis, the breast cancer tumor genotype frequencies of single nucleotide polymorphisms (SNPs) in seven VEGF and VEGF receptor genes were determined from patient formalin fixed paraffin embedded tissue blocks (FFPE). Patients whose tumors possessed a VEGF (-2578 AA) or a VEGF (-1154 AA) genotype had a marked statistically significant improvement in median overall survival in association with bevacizumab therapy (-2578 AA genotype HR 0.58 p=0.023, -1154 AA genotype HR 0.62 p=0.001) (Schneider et al., 2008). Furthermore, significant associations between hypertension and patients with the VEGF (-634 CC) genotype (p=0.005) and the VEGF (-1498 TT) genotype (p=0.022) were also observed. Confirmation of these observations is planned in a prospective large randomized phase III trial testing the role of bevacizumab in addition to standard chemotherapy for breast cancer patients in the adjuvant setting. Lastly, investigators have also observed associations between the development of treatment related hypertension and favorable clinical outcomes in patients treated with VEGF directed therapies (Bono et al., 2011). To date, no predictors of response to VEGF directed therapy have been examined or reported in bladder cancer. Therefore as additional secondary objectives of this trial we plan to assess associations between improved biologic and clinical outcomes according to VEGFR over-expression, host VEGFR mutation, and treatment related hypertension status.

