    - c. LVEF assessed by 2-D echocardiogram (ECHO)  $<$  50% or lower limit of normal (whichever is higher) or multiple gated acquisition scan (MUGA),  $<$  45% or lower limit of normal (whichever is higher)
    - d. Any of the following within 6 months prior to starting study drug: myocardial infarction (MI), severe/unstable angina, Coronary Artery Bypass Graft (CABG), Congestive Heart Failure (CHF), Cerebrovascular Accident (CVA), Transient Ischemic Attack (TIA), Pulmonary Embolism (PE)
    - e. Uncontrolled hypertension defined by a SBP  $\geq$  160 mm Hg and/or DBP  $\geq$  100 mm Hg, with or without anti-hypertensive medication(s)
  - Impairment of gastrointestinal (GI) function or GI disease that may significantly alter the absorption of dovitinib (e.g. ulcerative diseases, uncontrolled nausea, vomiting, diarrhea, malabsorption syndrome, or small bowel resection)
  - Cirrhosis, chronic active hepatitis or chronic persistent hepatitis
  - Known diagnosis of human immunodeficiency virus (HIV) infection (HIV testing is not mandatory)
  - Patients who are currently receiving anticoagulation treatment with therapeutic doses of warfarin. Full-dose anti-coagulation with low molecular weight heparin is permitted.
  - Other concurrent severe and/or uncontrolled concomitant medical conditions (e.g. active or uncontrolled infection, uncontrolled diabetes) that could cause unacceptable safety risks or compromise compliance with the protocol

9. Pregnant or nursing (lactating) women, where pregnancy is defined as the state of a female after conception and until the termination of gestation, confirmed by a positive hCG laboratory test.
10. Women of child-bearing potential, defined as all women physiologically capable of becoming pregnant, unless they are using highly effective methods of contraception (defined below). Highly effective contraception must be used by both sexes (female patients and their *male partners*) *during study treatment and for 30 days after the last dose of study medication*.

Highly effective contraception methods include:

- Total abstinence (when this is in line with the preferred and usual lifestyle of the subject). Periodic abstinence (e.g., calendar, ovulation, symptothermal, post-ovulation methods) and withdrawal are not acceptable methods of contraception

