## 6.1.4 Treatment Interruption and Treatment Discontinuation

Toxicity intensity a	Dose modification b, c
Cardiovascular	
Hypertension	Treatment-emergent hypertension should be treated as per standard cardiology practice. Recommended agents for the management of blood pressure elevations on dovitinib include angiotensin-converting enzyme inhibitors and calcium channel blockers.
SBP < 160 mmHg and/or DBP < 100 mm Hg, with or without anti-hypertensive medication	Maintain dose level
SBP ≥ 160 mmHg and/or DBP ≥ 100 mm Hg, with or without anti-hypertensive medication, but not immediately life-threatening	Delay the study treatment and initiate/intensify antihypertensive therapy. Dovitinib may be restarted in conjunction with standard anti-hypertensive medication if BP is controlled (i.e. BP < 160/100 mmHg). Once BP is controlled after suspending dovitinib, maintain dose level or ↓ 1 dose level at the discretion of the investigator.
Life-threatening consequences (e.g., malignant hypertension, transient or permanent neurologic deficit, hypertensive crisis); urgent intervention	Discontinue study treatment permanently

Toxicity intensity a	Dose modification b, c
indicated	
Left ventricular systolic dysfunction	
Left ventricular ejection fraction (LVEF) $\geq$ 50%/LLN (ECHO), or $\geq$ 45%/LLN (MUGA)	Maintain dose level
LVEF $<$ 50%/LLN (ECHO), or $<$ 45%/LLN (MUGA), or Symptomatic due to drop in ejection fraction responsive to intervention	Delay study treatment until resolved to $\geq$ 50%/LLN (ECHO) or $\geq$ 45%/LLN (MUGA), then $\downarrow$ 1 dose level
Refractory or poorly controlled heart failure due to drop in ejection fraction; intervention such as ventricular assist device, intravenous vasopressor support or heart transplant indicated	Discontinue study treatment
Other cardiovascular	
Grade 1	Maintain dose level
Grade 2	Maintain dose level If asymptomatic decrease of LVEF by absolute value of 20% and to $<$ LLN, delay study treatment until resolved to $\leq$ grade 1, then $\downarrow$ 1 dose level
Grade 3	Delay study treatment until resolved to $\leq$ grade 1, then $\downarrow$ 1 dose level
Grade 4	Discontinue study treatment
Gastrointestinal	
Diarrhea	At the first sign of abdominal cramping, loose stools, or onset of diarrhea, it is recommended that the patient be treated according to institutional standard of care
Grade 1 (despite maximal anti-diarrheal medication)	Maintain dose level

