#### **10.7.1 Exploratory Objectives Statistical Hypothesis, Model, and Method of Analysis**

All exploratory objectives are hypothesis generating in nature. Pre- and post-treatment phosphorylation changes in FGFR and VEGFR pathways will be analyzed by paired t-tests. FGFR SNPs, VEGFR SNPs, post-treatment hypertension, and baseline clinical factors of interest (e.g. age, ECOG PS, Charlson Comorbidity Index, gender, T1 vs. CIS, number of prior intravesical therapies, etc.) will be analyzed by univariate logistic regression and Cox regression for significant associations with 6-month CR and 1-year RFS rates, respectively. No multivariate models will be adopted given the small sample size. Concordance rates between tumor, urine, and circulating free plasma FGFR3 mutations will be summarized by Goodman-Kruskal gamma. The post-treatment bladder tissue dovitinib concentrations will be summarized by mean, standard deviation, minimum, median, maximum, and boxplot. Transformations to normality will be considered when necessary.

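### The exploratory post-treatment hypertension variable ignores baseline blood pressure, so patients already at 140-159/90-99 mmHg on entry can count as on-drug cases

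*Combined protocol and SAP*

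**What the plan says.** The exploratory objective in 3.3 is "To characterize associations between post-treatment hypertension, 6-month complete response rate and 1-year relapse free survival rate in patients treated with dovitinib". The variable is defined in 3.3.1, and the synopsis and Table 3-1 repeat it. The definition opens "Hypertension will be defined as a systolic blood pressure (SBP) of", sets thresholds of 140 mmHg systolic or 90 mmHg diastolic, and requires only that the value be "recorded at any time after dovitinib therapy is initiated". It does not ask for a normal baseline, a rise from baseline, or a change in antihypertensive medication.

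Four other places bear on it:

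- Section 1.2.3 cites reports linking hypertension that develops under VEGF-directed therapy with better outcomes, and plans to assess outcomes by "host VEGFR mutation, and treatment related hypertension status".
- Section 5.2, exclusion 8 item e, begins "Uncontrolled hypertension defined by a SBP" and sets the limit at 160 systolic and/or 100 diastolic, whether or not the patient takes antihypertensives.
- Section 6.1.4 states "Treatment-emergent hypertension should be treated as per standard cardiology practice". Its row on starting or intensifying antihypertensive therapy begins at 160/100.
- Section 10.7.1 enters "FGFR SNPs, VEGFR SNPs, post-treatment hypertension, and baseline clinical factors of interest" one at a time into logistic regression for 6-month complete response (CR) and Cox regression for relapse-free survival (RFS). It rules out multivariable models because the sample is small.

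**The concern.** A variable meant to capture a drug effect should separate hypertension that appears on the drug from hypertension the patient brought to the trial. This one does not. A patient with a systolic pressure of 140-159 or a diastolic pressure of 90-99 at entry is eligible, and one unchanged reading after the first dose makes that patient a case. The comparison in 10.7.1 then mixes new-onset and pre-existing hypertension in one group, and no term in the model can separate them.

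What is at stake is the reading of a hypothesis-generating result. A real link between drug-induced hypertension and response could be diluted, or an apparent link could partly reflect who was hypertensive on entry. The problem is separate from the open-ended time window: it would remain if only early readings were used.

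**Working it through.** The plan attaches no sample size, power or expected rate to this variable, so there is no stated figure to reproduce. The check is a comparison of the text followed by an illustration.

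**Text.** The case threshold is 140/90 (3.3.1) and the entry limit is 160/100 (5.2). The band between them is open at entry and counts as hypertension on treatment. Baseline blood pressure is collected (7.5, 7.10.4) but used neither in the definition nor in the model (10.7.1).

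**Inputs for the illustration.**

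- N = 20 (10.8).
- b = share of patients at or above 140/90 at entry. The documents give none; assumed 10%, 30% and 60%.
- h = new-onset rate among the rest. The only figure in the documents is the 14.3% hypertension adverse-event rate for the 5-days-on/2-days-off schedule (1.2.2, cardiovascular system). An adverse-event rate may understate the proportion with any single reading at 140/90, so 30% and 50% are also assumed.
- Each patient raised at entry is assumed to have at least one on-study reading at or above the threshold.

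**Formulas.** Pre-existing = 20 × b. New-onset = 20 × (1 − b) × h. Pre-existing share = pre-existing / (pre-existing + new-onset).

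| b | Pre-existing | New-onset at h = 14.3% / 30% / 50% | Pre-existing share |
|---|---|---|---|
| 10% | 2 | 2.6 / 5.4 / 9.0 | 44% / 27% / 18% |
| 30% | 6 | 2.0 / 4.2 / 7.0 | 75% / 59% / 46% |
| 60% | 12 | 1.1 / 2.4 / 4.0 | 91% / 83% / 75% |

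For example, with b = 30% and h = 30%: 6 / (6 + 4.2) = 59%.

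**Effect on the association.** Assume CR is 50% with new-onset hypertension and 15% in everyone else, including patients raised at entry. The true odds ratio is (0.50/0.50) / (0.15/0.85) = 5.7. With h = 30% and b = 30%, the new-onset fraction is 0.7 × 0.3 = 0.21. CR among counted cases is (0.21 × 0.50 + 0.30 × 0.15) / (0.21 + 0.30) = 0.150/0.51 = 29%. The odds ratio becomes (0.294/0.706) / (0.15/0.85) = 2.4. The same steps give 3.9 at b = 10% and 1.7 at b = 50%. If entry hypertension were itself related to outcome, the distortion could go either way.

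**The smaller gap.** One recorded reading at 140/90 makes a permanent case, so later control does not undo it. A case is missed only if a rise is treated without any recorded value at or above the threshold, for instance when it is found and managed between visits. This was not sized, because the documents give nothing to size it with.

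**The case against.** The best defence is that the working sections are consistent with each other. Sections 3.3, 10.7 and 10.7.1 and Table 3-1 all speak of post-treatment hypertension, and the definition fits that label. The treatment-related meaning comes only from the background in 1.2.3. This stands as a point about wording. But 1.2.3 is where the plan says why the variable is of interest, and the definition does not measure that.

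Baseline is also used elsewhere. Section 10.6.3.4 plans a vital-signs shift table from baseline to worst value, 10.6.3.2 counts adverse events that begin or worsen after baseline, and 10.1 allows further exploratory analyses. None of these is tied to the CR and RFS association.

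Three stronger readings might be inferred, and the documents do not support them:

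- *The analysis would mainly compare patients hypertensive at entry with the others.* That depends on an unknown baseline prevalence and on an adverse-event rate used as a proxy. Under several assumed inputs, pre-existing cases are a minority.
- *New cases controlled by medication are generally missed.* A reading that reaches the 160/100 row in 6.1.4 has already passed 140/90, and once recorded it counts for good.
- *A spurious link through age or comorbidity should be expected.* This is conjecture. Age and the Charlson index are themselves examined univariately in 10.7.1.

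**Conclusion.** The point holds for an exploratory analysis. As defined, the variable counts unchanged pre-existing hypertension as an on-treatment event, and the planned models do not adjust for it. Pre-existing cases would be about 18% of the group in the most favourable combination of assumptions shown and 91% in the least favourable. Both the entry prevalence and the new-onset range are assumptions; only the 14.3% comes from the documents, and it measures something slightly different. The defensible conclusion is that the association may be diluted or may partly reflect entry hypertension, not that it will be. Missed cases are a minor, unquantified addition. No alpha, power or decision depends on this variable, and the 6-month CR estimate is untouched. This is a cheap improvement.

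**What to change.** For the 10.7.1 analyses, and in 3.3.1, Table 3-1 and the synopsis:

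1. Define treatment-emergent hypertension as baseline below 140 systolic and below 90 diastolic, with a later recorded reading of at least 140 or at least 90. State which pre-dose reading is the baseline.
2. Report patients at or above 140/90 at baseline as a separate group. Alternatively, count them only if they have a hypertension adverse event recorded as starting or worsening after baseline, which is the rule already used in 10.6.3.2.
3. Keep the present definition as a sensitivity analysis.
4. Optionally, count new or increased antihypertensive medication. Section 6.1.5 requires medications to be recorded but does not say that the indication is, so check the eCRF first.

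This changes an analysis variable only and sets no clinical rule. Items 1 to 3 need wording and programming, because blood pressure and adverse events are already collected. The real cost is small numbers. On the assumptions above there would be about 1 to 9 treatment-emergent cases, with about 5 complete responses expected at the 25% design rate (20 × 0.25). Estimates will be imprecise and should be reported descriptively.

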**Table 3-1 Objectives and related endpoints**

	Objective	Endpoint	Analysis
Primary	
 
• To determine the 6-month complete response rate in BCG-refractory UC patients with FGFR3 mutant or overexpressing tumors treated with dovitinib
 
	
 
• 6-month complete response rate
 
	Refer to Section 10.5
Key secondary	
 
• To determine the 1-year relapse free survival rate defined in BCG-refractory UC patients treated with dovitinib
 
• To determine the rate of
 
	
 
• 1-year relapse free survival rate
 
	Refer to Section 10.6

Objective	Endpoint	Analysis
	
 
progression to muscle-invasive stage (i.e. T2-T4)
 
To determine 3- and 6-month partial response rate defined as a reduction in T-stage on post-therapy TURBT (i.e. T1 -> Ta; T1+Tis -> Tis)
 
To characterize treatment related toxicity rates assessed by CTCAE v4.0
 
	
 
Muscle-invasive progression rate
 
3- and 6-month partial response rate
 
Treatment related toxicity rates
 

Exploratory	
 
To characterize pre- and post-treatment bladder tumor FGFR pathway phosphorylation changes
 
To characterize associations between pre-treatment germline (as assessed by PBMC extracted DNA) FGFR SNPs and post-treatment 6-month complete response rate and 1-year relapse free survival rate in patients treated with dovitinib
 
To characterize pre- and post-treatment VEGFR pathway phosphorylation changes as assessed by bladder tumor tissue immunohistochemistry
 
To characterize associations between pre-treatment germline (as assessed by PBMC extracted DNA) VEGFR SNPs and post-treatment 6-month complete response rate and 1-year relapse free survival rate in patients treated with dovitinib
 
To characterize associations between post-treatment hypertension 6-month
 
	
 
Pre- and post-treatment bladder tumor FGFR pathway phosphorylation changes will be assessed by bladder tumor tissue immunohistochemistry utilizing commercially available antibodies including, but not limited to, the following: FGFR3, pFGFR3, VEGFR2, pVEGFR2, FRS2, pFRS2, ERK, pERK
 
Pre-treatment germline FGFR SNPs will be assessed by testing extracted DNA from patient PBMC's (collected prior to initiating dovitinib therapy) with validated commercial probes
 
Pre- and post-treatment bladder tumor VEGFR pathway phosphorylation changes will be assessed by bladder tumor tissue immunohistochemistry utilizing commercially available antibodies including, but not limited to, the following: FGFR3, pFGFR3, VEGFR2, pVEGFR2, FRS2, pFRS2, ERK, pERK
 
Pre-treatment germline VEGFR SNPs will be assessed by testing extracted DNA from patient PBMC's (collected prior to initiating dovitinib therapy) with validated commercial probes
 
Hypertension will be defined as a systolic blood pressure (SBP) of <math>\geq</math> 140 mmHg or a
 
 
Refer to Section 10.7

[figure not shown]
Objective	Endpoint	Analysis

complete response rate and 1-year relapse free survival rate in patients treated with dovitinib
 
 
• To characterize concordance rates between UC patient detected tumor, urine and circulating free plasma FGFR3 mutations
 
• To characterize post-treatment bladder tissue dovitinib concentrations
 
• To characterize VEGFR over-expression status within tumor tissue
 
	
diastolic blood pressure (DBP) of <math>\geq</math> 90 mm Hg recorded at any time after dovitinib therapy is initiated
 
Presence of FGFR3 mutation within patient tumor tissue, urine, will be assessed by massive parallel sequencing analysis of exons 7, 10, and 15 utilizing Ion Torrent PGM instrument. Presence of FGFR3 mutation within patient free plasma will be assessed by PCR-amplification of the target regions and sequencing
 
Post-treatment bladder tissue obtained at 3-month TURBT will be analyzed by IUSCC Clinical Pharmacology Analytical core according to standard commercial assays
 
Presence of VEGFR over-expression within tumor tissue will be assessed by standard IHC analysis
	

## 4 Investigational Plan

### 4.1 Study Design

This trial will be a single-arm, non-randomized, multi-center, phase II study conducted through Hoosier Cancer Research Network assessing the 6-month complete response rate and toxicity profile of oral dovitinib therapy in BCG-refractory urothelial carcinoma patients with tumors with FGFR3 mutations or over-expression who are ineligible for or refusing cystectomy. A sample size of 20 evaluable patients receiving dovitinib therapy is expected (up to 50 patients screened). Study design is shown in Figure 4-1. This study will characterize the clinical relevance and viability of FGFR3 and VEGFR as therapeutic targets in this biologically enriched population. Furthermore, due to the routine acquisition of pre- and post-treatment bladder biopsies as standard of care practice, this trial will significantly enhance identification and development of prognostic and predictive dovitinib biomarkers.

